6.7 Safety Plan

To ensure subject safety a Safety Plan is in place describing the study specific safety measures that are to be taken during the study. This Safety Plan must be used in conjunction with this protocol.

The purpose of the Safety Plan is to ensure:

- the safety of patients receiving etanercept, Diamyd and vitamin D treatment in the study.
- that appropriately qualified medical personnel are readily available to advise on trial related medical questions or problems regarding the study drug treatment in the above mentioned study.
- that study personnel are educated about know side effects of the study drug treatment and how to handle them.
- that patients and their parents/legal guardian(s) are given information about possible side effects.

6.7.1 General precautions during etanercept treatment (see Safety Plan for details)

To detect infections and other side effects as early as possible it is very important the investigator/study team cautiously collects symptoms and signs indicating any of the withdrawal criteria, as well as adverse events, and also be responsive to any spontaneous symptom/adverse event reporting in between study visits and at study visits. Patients who develop a new infection under etanercept treatment should be closely monitored. Fever is one of the first signs of infections.

The Medical Adviser will be contacted and the etanercept treatment will be interrupted, until a decision is taken by the responsible physician to continue or withdraw, if a patient during etanercept treatment develops or experiences

- Fever, long-lasting and/or low-grade
- Infection with fever

- Sore throat, especially with fever
- Fever with any kind of symptoms e.g. symptoms from a joint, red skin, difficulties to breath, abnormal tiredness
- Unexpected productive cough lasting two-three weeks or more
- Any abnormal signs such as pronounced tiredness, paleness, difficulties to breath, hematomas in the skin, bleedings, bruises, weight loss or any worrying symptom or sign
- Suspicion of exposure to tuberculosis or symptoms or signs of tuberculosis
- Suspicion of exposure to Varicella Zoster virus or symptoms or signs of chickenpox/shingles

All patients and their parent(s)/legal guardian(s) must be informed by the investigator and study team that they should seek medical help immediately in case the patient treated with etanercept develops signs and/or symptoms of blood dyscrasia or infections (long-lasting low-grade fever, sore throat, bruises, bleedings, weight loss, unexpected productive cough lasting two-three weeks or more and/or paleness).

Since fever is one of the first signs of infection, all patients and their parent(s)/legal guardian(s) will be informed to, during etanercept treatment, carefully follow the patient's general condition, and if affected, to measure the patient's morning body temperature daily, and in case it is elevated also measure it at least once more that day. The body temperature should be documented in the patient diary and the study team should be contacted.

As there are reports that the risk for hypoglycemia may increase in patients with diabetes being treated with etanercept, there should be extra awareness among the diabetes team members and among patient and parent(s)/legal guardian(s) regarding the possible need to decrease insulin doses.

It is desirable that patients that are to start with etanercept treatment have followed the national vaccination program. Live vaccines must not be given during etanercept treatment.

6.7.2 General precautions during Vitamin D treatment

Blood draws for Vitamin D will be taken at screening (Visit 1), month 1 (Visit 3), month 6 (Visit 6), month 9 (Visit 7) and month 15 (Visit 8) and be analyzed continuously. Blood draws for Calcium will be taken at every visit. Should the blood concentration during Vitamin D treatment exceed 125 nmol/L or if the child would develop hypercalcemia, the Vitamin D treatment will be stopped. The subject will however continue in the study and complete all the other study related evaluations, including sampling for Vitamin D and Calcium levels.

Vitamin D treatment will be started again if the levels fall <100 nmol/L.

Vitamin D treatment will be stopped and not started again if the subject develops hypercalcemia.

6.8 Data Safety Monitoring Board (DSMB)

An independent Data Safety Monitoring Board (DSMB) will be appointed. A DSMB charter will be written to outline the working procedures and the duties of the DSMB. The DSMB will review the safety twice per year as long as patients are being treated with etanercept and thereafter annually.

6.9 Adverse Events

See section 9.2.2 below.

6.10 Concomitant Medication

Any concomitant medication used during the study, whether considered relevant for the study or not by the investigator must be reported on the concomitant medication log of the CRF. Please also see section 8.5, below.

7

7 Scheduling of Procedures Table 2. Pilot EDCR IIa Study, Schedule of Study Events, DIABETES patients

Study Period	Scree- ning	Intervention Main Study Period			Follow-up Extension Study Preiod				
Visit number	1	2	3	4	5	6	7	8	9
Day from Baseline (Visit 2)	D	D1	M1	M2	M3	M 6	M9	M 15	M30
(Day/Month)	-10 to		(D30	(D60	(D90	(D180	(D270	(D450	(D900
	-21		± 3)	± 3)	± 7)	± 7)	± 14)	± 14)	±14)
Informed Consent	Х								
Inclusion/Exclusion Criteria	Х								
Etanercept Administration starts		Start			Stop				
·		Day 1			Day 90				
Vitamin D administration starts		Start Day 1						Stop Day 450	
GAD-Alum (Diamyd) injections			Х	Х					
Medical History	Х								
General Physical Examination	Х					Х	Х	Х	Х
Brief Physical Examination		Х	Х	Х	Х				
Neurological Examination	Х					Х	Х	Х	Х
Concomitant Medication	Х	Х	Х	Х	Х	Х	Х	Х	Х
Weight, height, BMI	Х	Х	Х	Х	Х	Х	Х	Х	Х
Urine pregnancy test (females)	Х	Х	Х	Х	Х	Х	Х	Х	Х
Injection site inspection ^a			Х	Х					
Insulin dose		Х	Х	Х	Х	Х	Х	Х	Х
Self-Reported Severe		Х	Х	Х	Х	Х	Х	Х	Х
Hypoglycemia ^b		[ 						
Adverse Events		Х	Х	Х	Х	Х	Х	Х	Х
Patient Diary review and collection			х	Х	Х	х			
Screening for tuberculosis, including blood tests, medical history and pulmonary X-ray	Х								
Screening for Hepatitis B and C (blood tests)	Х								
Blood sampling for safety			-						
Hematology	Х	Х	Х	Х	Х	Х	Х	Х	Х
Chemistry, including Calcium	Х	Х	Х	Х	Х	Х	Х	Х	Х
Urinalysis									
Microalbuminuria	Х	Х	Х	Х	Х	Х	Х	Х	Х
Creatinine	Х	Х	Х	Х	Х	Х	Х	Х	Х
Blood sampling for Auto-antibod									
GADA	Х	Х	Х	Х	Х	Х	Х	Х	Х
Other diabetes-related		Х	Х	Х	Х	Х	Х	Х	Х
autoantibodies	6	L	L			L		L	L
Blood sampling for Diabetes stat			N/	N N	N/		N/	N/	v
HbA1c	X	X	X	X	X	X	X	X	X
Fasting glucose/C-peptide	Х	X	Х	Х	Х	X	Х	X	X
MMTT glucose/ C-peptide		Х				Х		Х	Х
Blood sampling for genetics						1			
HLA Blood compliant for immunology		Х							
Blood sampling for immunology TNF-alfa, IL-1 beta, IL-2, IL-17,		Х	Х	Х	Х	Х	Х	Х	Х
		^	^	^	^	^	^	^	^
IL-5,10, 13 IFN-gamma and T-regulatory									
IFN-gamma and T-regulatory cells									
IFN-gamma and T-regulatory cells Blood sampling for viruses							X		
IFN-gamma and T-regulatory cells Blood sampling for viruses Enteroviruses ^c		X	Х	Х	X	X	Х	X	Х
IFN-gamma and T-regulatory cells Blood sampling for viruses Enteroviruses ^c Blood sampling additional		-				-			
IFN-gamma and T-regulatory cells Blood sampling for viruses Enteroviruses ^c	X	X	X X X	X	X	X X X	X X X	X X X	X

^a Inspection of injection site before and 60 minutes after GAD-Alum injection by investigator or nurse

^b Severe Hypoglycemia is defined as needing help from others and/or seizures and/or unconscious
 ^c Especially certain types of Coxsackie virus may play a role for the beta cell destruction. Details will depend

on results in the ongoing DIABGAD trial.

7.1 Visits

The first visit, the screening visit (Visit 1) should be performed 10 to 21 days before planned Visit 2 (Baseline). Visit 3 and 4 should then be scheduled with a visit window of \pm 3days (first and second injection with GAD-Alum) and of \pm 7 days for Visit 5 and 6. For Visit 7, 8 and 9 the visit window is extended to \pm 14 days.

Please note that all visits, except Visit 4 must be calculated from the baseline visit (Visit 2) according to the visit schedule. For Visit 4 (second GAD-Alum administration) the visit date must be set in accordance with Visit 3 (i.e. the first GAD-Alum administration) so that the first and second GAD-Alum doses will be 30 days apart (\pm 3 days). Please also note that the visits must be performed within the visit windows to comply with the study protocol.

8 Study Medication

8.1 Study Medications

The following medication supplies will be used in the study:

A. Study medication:	GAD-Alum (Diamyd) subcutaneous injection Dosage and interval: 20 µg will be given subcutaneously at two occasions with one month interval (at Days 30 and 60).
IMP supplier:	Diamyd Medical AB, Stockholm, Sweden.
B. Study Medication	Etanercept (Enbrel) Dosage and interval: 0.8 mg/kg body weight, max 50 mg, given subcutaneously once per week from Day 1-90
IMP supplier	Commercially available
C Study Medication	Vitamin D (Calciferol) in oral solution Dosage and interval: 2 000 IU daily for 450 days
IMP supplier	Commercially available

8.2 Supply, Packaging, Handling and Storage

GAD-Alum (Diamyd) will be a subcutaneous formulation, supplied by Diamyd Medical. It will be supplied as pre-packed medication from Diamyd Medical to central pharmacy who will then distribute to the clinical site or local pharmacy. All dosing will take place in the hospital, and handled only by trained and authorised study personnel.

GAD-alum must be stored in a refrigerator at 2-8 °C in a secure area (e.g. a locked cabinet or drug storage room), protected from unintended use.

Etanercept will be handled and distributed by Apoteket AB who will then distribute to the clinical site or local pharmacy.

Vitamin D (Calciferol) will be handled and distributed by Apoteket AB, who will then distribute to the clinical site or local pharmacy.

All study medication will be labelled with information according to local regulation.

8.3 Dosage and Administration

Etanercept	0.8 mg/kg body weight (max 50 mg) given subcutaneously once weekly from Day 1-90
Vitamin D	2 000 IU per day, given per os from Day 1 to Day 450
GAD-Alum:	$20 \ \mu g$ given subcutaneously in the stomach area two times with one month interval.

8.4 Duration of Treatment

See 8.3

8.5 Concomitant Medication

No systemic immune modulating medication, no other diabetes medication than insulin, and no vitamin D, whether marketed or not, are allowed.

8.6 Study medication Accountability

All study medications supplied for this study must be retained in a safe place at all times of the study. Only personnel authorised by the investigator should dispense the study medication, and the accountability is the responsibility of investigator.

A study medication inventory (dispensing records) for all medication dispensed must be maintained at all times and always kept current. Used and unused medication must be stored at the site or pharmacy throughout the study. The investigator/pharmacist must keep record of all study drugs received, used and returned. Both pharmacies and study sites are obliged to properly measure and record the storage temperature.

When the study is completed all unused and used study medication containers must be returned to the drug supplier unless the drug supplier has approved other arrangements.

9 **Response Variables and Outcomes**

9.1 Assessments

9.1.1 Variables

The tolerability and safety assessments includes occurrence of adverse events (AEs), laboratory measurements, physical examinations and neurological assessments (See section 6.3-6.7)

Adverse events will be recorded by the physician at every visit throughout the study.

Blood tests for safety:

- Chemistry: Creatinine, Calcium, Liver function tests (alanine aminotransferase [ALT], Aspartate Aminotransferase [AST], Alkaline Phosphatase, Bilirubin)
- Haematology (MHC, MCV, MCHC, Hemoglobin, Platelets, Leukocytes)

Urinalysis for safety:

- Urine pregnancy test as appropriate
- Microalbuminuria
- Creatinine

Other Variables which will be evaluated:

- Inflammatory markers, especially TNF-alfa, IL-1 beta, IL-2, IL-17
- Th2-deviation of cell-mediated immune response seen e.g. as increased ratio of IL-5,10, 13 in comparison with IFN-gamma, TNF-alfa, IL-1 beta and IL-17, and increase of T-regulatory cells
- C-peptide (90 minute value and AUC_{mean 0-120 min}) during an MMTT
- Proportion of patients with a stimulated maximum C-peptide level above 0.2 nmol/L
- Fasting C-peptide
- Hemoglobin A1c (HbA1c)
- Exogenous insulin dose per kg body weight and 24 hours
- Vitamin D levels in serum

Outcomes above are in agreement with the general Guidelines for Intervention Trials in subjects with newly diagnosed T1D defined by the Immunology of Diabetes Society (89).

9.2 Adverse events, Serious Adverse Events and Pregnancy

9.2.1 Definitions of Adverse Events (AE)

An Adverse Event (AE) is defined as any untoward medical occurrence in a subject during a clinical study administered a medicinal product and which does not necessarily have a causal relationship with this treatment(s).

An AE can therefore be any unfavorable and unintended clinical sign or symptom, any illness or disease, which develops or worsens in intensity during the course of the trial. It also includes an

abnormal laboratory finding, if e.g., the abnormality results in trial withdrawal, is serious, is associated with clinical signs or symptoms, or is considered being of clinical relevance.

It could also include accidents and reasons for changes in medication (drug and/or dose), any medical/nursing/pharmacy consultation and admission to hospital/surgical operations.

Any new findings, clinically significant laboratory values or worsening of pre-existing condition must be reported as an AE by the investigator, whether or not considered related to the medicinal product(s).

Note that hospital admission and/or surgical operations for illness, which existed before the study drug was given or the subject was enrolled in the clinical trial and did not worsen during the study, are not AEs.

9.2.2 Seriousness

A Serious Adverse Events (SAE) is defined as: an Adverse Event that is fatal, life-threatening, significant or persistent disabling or requires hospitalisation or prolongation of exisiting hospitalisation, a congenital anomaly or birth defect.

These characteristics/consequences have to be considered at the time of the event. For example, regarding a life- threatening event, this refers to an event in which the subject was at risk of death at the time of the event; it does not refer to an event which hypothetically might have caused death if it were more severe.

Some medical events may jeopardise the subject or may require an intervention to prevent one of the above characteristics/consequences. Such events (referred to as *important medical events*) should also be considered as serious in accordance with the definition.

9.2.3 Intensity

Mild:	the Adverse Event is transient and easily tolerated.	
Moderate:	the Adverse Event causes the patient discomfort and interrupts the patient's usu	
	activities.	
Severe:	the Adverse Event causes considerable interference with the patient's usual	
	activities, and may be incapacitating or life-threatening.	

Note: a distinction should be drawn between serious and severe AEs. The term severe is used to describe the intensity of the event and the event does not necessarily need to be considered serious. The term serious is based on the patient/event outcome or action and serves as a guide for defining regulatory reporting obligations.

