5.4 Patient Withdrawal

In accordance with the Declaration of Helsinki, the investigator must explain to the patient that they have the right to withdraw from the study at any time, and that this will in no way prejudice their future treatment. The reason for any kind of withdrawal must be recorded on the appropriate CRF.

There will be two main categories for withdrawals from the study:

Complete withdrawal (i.e. stopping investigational product and also continued efficacy and safety evaluations)

Standard reasons for withdrawing from further participation in the study and from the follow-up visits (and <e.g. blood tests>) may be:

- Patient's decision (withdrawal of consent to participate)
- Patient lost to follow-up

Withdrawals from investigational product (i.e. stopping one or several investigational products, but continuing follow-up visits, including efficacy and safety evaluations)

Standard reasons from withdrawing from taking further investigational product, but continuing follow-up visits and safety evaluations may be:

- Unacceptable adverse events
- Patient request
- Investigator's discretion
- Patient lost to follow-up/non-attendance
- Intercurrent illness
- The patient becomes pregnant

Thus subcutaneous GAD-Alum should not be given to the patient if the patient after inclusion in the study develops/experiences

- Brain damage, epilepsia, head trauma, neurological disease
- Any active, serious hormonal disease other than T1D
- Other severe autoimmune disease (except celiac disease which is accepted for inclusion.)
- Immune-suppressive treatment
- Cancer, cancer treatment
- Any other diabetes drugs other than insulin
- Any vaccination
- Drug/alcohol abuse
- Become pregnant or is no longer willing to use safe contraceptives during the study

Etanercept should not be continued if the patient after inclusion in the study develops/experiences

- Allergic reactions to etanercept or any of the excipients
- Other severe reactions to etanercept injections
- Sustained elevations of creatinine of liver function tests,
- Evidence of cardiac disorder
- Severe infections, such as sepsis, meningitis or osteomyelitis

- Suspected, latent or manifest tuberculosis
- Suspected or manifest viral hepatitis
- Severe lymphopenia
- Anemia
- Thrombocytopenia
- Malignancy
- Urticaria
- Varicella Zoster virus exposure or infection
- Live vaccines such as morbilli, parotitis, rubella, live polio, BCG and others

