9.2.5 Reporting of Adverse Events

All Adverse Events must be recorded in the CRF, defining relationship to study medication, severity and seriousness. Adverse Events should also be recorded by the investigator in the patient file/notes.

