10.3 Statistical Analysis Plan

In brief the following analysis is planned:

All continuous variables will have the following descriptive statistics displayed: number of observations (n), mean value, standard deviation, minimum, median, and maximum. All variables Confidential

of a categorical nature will be displayed with frequencies and percentages. The tabulation of the descriptive statistics will be split by treatment group and visit. Where appropriate, baseline (screening) descriptive statistics will also be included.

Demographic and other baseline characteristics

Demographics such as age and gender will be described for Intention-to-treat and the Total population. Measures for other baseline characteristics are medical history, current medical conditions (at baseline), and current diabetes medication (at baseline). The baseline characteristics will be presented for the safety population. Demographics and baseline characteristics will be presented using descriptive statistics (summary tables).

Variables:

The AE/SAE data will be presented using a standardized tabulation of the frequency and incidence rate of all observed AEs/SAEs. The frequencies and incidence rates are calculated on a per patient basis. Adverse events will be summarized by body system, causality, and severity. Other safety data will be presented by descriptive statistics. Data regarding C-peptide and immune system as well as Adverse events and other safety data will be summarized descriptively.

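### The AE intensity scale in 9.2.3 leaves gaps and has no laboratory criterion, so lasting or symptom-free AEs cannot be graded consistently and the AE-by-severity table may misstate them

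*Combined protocol and SAP*

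**What the plan says.** Four parts of the combined protocol and SAP bear on this.

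- **9.2.1** brings laboratory findings into the AE definition: "Any new findings, clinically significant laboratory values or worsening of pre-existing condition must be reported as an AE by the investigator". Associated signs or symptoms are only one of several alternative reasons for counting an abnormal result, so symptom-free laboratory AEs are foreseen.
- **9.2.5** requires a grade each time: "All Adverse Events must be recorded in the CRF, defining relationship to study medication, severity and seriousness".
- **9.2.3** gives the only scale. Mild: "the Adverse Event is transient and easily tolerated". Moderate: discomfort plus interruption of usual activities. Severe: "the Adverse Event causes considerable interference with the patient's usual" "activities, and may be incapacitating or life-threatening". No laboratory threshold appears.
- **10.3** uses the result: "Adverse events will be summarized by body system, causality, and severity".

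Two further places matter. Section 5.4 lists sustained creatinine or liver-test elevations and "Severe lymphopenia" among the reasons for not continuing etanercept. Section 4.2.1 makes AE occurrence and laboratory measurements separate primary tolerability variables.

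**The concern.** The plan requires a grade for events that its scale does not cover. The protocol itself foresees laboratory changes that last, and *sustained* is the opposite of *transient*. If such a change causes no discomfort and interrupts nothing, it meets neither Mild nor Moderate. A large but symptom-free fall in platelets that soon recovers meets Mild, the same grade as a trivial one.

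Tolerability is the primary endpoint, severity is one of three named AE breakdowns, and section 3 says that the results will inform the design of a larger Phase II trial. About 20 patients at about 10 sites (6.1) is roughly two patients per site. Each investigator would settle the ungraded cases alone, and site habits could not be told apart from real differences.

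**Working it through.** The plan states no figure to reproduce. The check is whether the three definitions cover the events that they must grade.

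**Inputs (9.2.3).** T = transient; E = easily tolerated; D = discomfort; I = interference with usual activities (0 none, 1 interrupts, 2 considerable); L = life-threatening.

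- Mild = T and E
- Moderate = D and I ≥ 1
- Severe, strict reading = I = 2 (the life-threatening clause only describes such events)
- Severe, lenient reading = I = 2 or L (the clause is enough alone)

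**Combinations.** Leave out E together with D or I > 0, as contradictory. For each of the 2 × 2 values of T and L there remain 1 (E present) + 2 × 3 (E absent) = 7, so 4 × 7 = 28.

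**Ungraded, strict.** With E absent, three D/I pairs fail every definition: no discomfort and I = 0; no discomfort and I = 1; discomfort and I = 0. That gives 3 × 4 = 12. With E present but T absent there are 2 more. Total 12 + 2 = **14 of 28**.

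**Ungraded, lenient.** Every L combination is now Severe. The rest give 3 × 2 + 1 = **7 of 28**.

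These count logical cells, not expected events. The cells that matter most here are:

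| Event | Strict | Lenient |
|---|---|---|
| Symptom-free, transient, well tolerated, not life-threatening | Mild | Mild |
| Symptom-free, lasting, well tolerated, not life-threatening | none | none |
| Symptom-free, transient, well tolerated, life-threatening | Mild | Mild and Severe |
| Symptom-free, lasting, well tolerated, life-threatening | none | Severe |
| Discomfort without interruption, not life-threatening | none | none |

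The second and fifth rows fail on both readings. In the first two rows the size of the laboratory departure plays no part.

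**Scope.** Of the 21 etanercept items in 5.4, 6 rest wholly or mainly on laboratory results: sustained creatinine or liver-test elevation, lymphopenia, anaemia, thrombocytopenia, pancytopenia or aplastic anaemia, and impaired renal or liver function. Section 9.1.1 lists 6 chemistry + 6 haematology = 12 blood safety analytes, and serum vitamin D is measured too. These counts show where the gap can bite, not how often.

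**Leverage.** One patient in 20 is 1/20 = 5 percentage points.

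**After the fix below.** I = 0 gives Mild, I = 1 Moderate, and I = 2 or L Severe, with the highest grade met applying. All 28 combinations are graded.

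**The case against.** The case that this is minor has real substance.

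- **Severe is broader than interference.** A reader might infer that a symptom-free laboratory event can never be Severe. That needs the strict reading; an investigator could rely on the life-threatening clause. The objection stands for life-threatening values and leaves those short of that untouched.
- **The direction is unknown.** A reader might infer that the table understates laboratory toxicity. An event with no fitting grade may be graded up, graded down or left blank, so the documents do not support a direction.
- **Other outputs carry the information.** AE occurrence does not depend on grade. Laboratory values and injection-site reactions are primary variables in their own right; 10.3 gives minimum and maximum by visit; 10.4 lists all patients' data and the reasons for withdrawal; and 9.2.2 lets important medical events count as serious. So the data would not be concealed. But the planned summaries do not count patients with a marked or lasting abnormality, and 9.2.3 itself separates serious from severe, so neither route repairs the severity column.
- **"Severe lymphopenia" in 5.4 is not a contradiction.** There the adjective describes the size of a laboratory finding; in 9.2.3 it describes AE intensity. That is right. It shows only that the protocol uses a laboratory sense of severity that the scale does not provide.
- **Unseen documents.** The Safety Plan and the CRF guidance might hold grading rules, and 10.3 calls itself brief. This limits certainty, although the purposes stated for the Safety Plan in 6.7 do not include AE grading.

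**Conclusion.** The point holds in a limited form. On either reading of Severe, a lasting, well-tolerated, non-life-threatening AE has no grade, and a symptom-free laboratory AE short of life-threatening cannot exceed Mild. Since 9.2.5 demands a grade and 10.3 tabulates it, this is a defect in a stated rule and not merely missing detail.

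The consequence is confined to the AE-by-severity summary, which is one descriptive breakdown and is not itself named as an endpoint. Its size cannot be computed. A reader might suppose 1 to 3 affected patients, and so 0% severe shown where 5% to 15% belongs. That would assume the number of events, that each is truly severe on a scale nobody has named, and that each is graded down; the documents support none of these.

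The conclusion rests on reading the definitions as written and on no separate grading instruction existing in the documents that are not available.

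**What to change.** In 9.2.3:

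1. Delete *transient* from Mild, so that duration does not decide the grade.
2. Make the grades exhaustive: Mild does not interrupt usual activities; Moderate interrupts them; Severe interferes considerably, or is incapacitating or life-threatening. Keep that last wording: without it, a dangerous but symptom-free event that is not a laboratory finding would fall to Mild. State that the highest grade met applies.
3. Grade laboratory AEs by the size of the departure from the age-appropriate reference range, on one published scale named and fixed before the first table is produced.

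In 10.3, tabulate laboratory AEs by that grade. Apply it only to analytes in 9.1.1 that are measured. Lymphopenia cannot be graded from the listed safety tests, because 9.1.1 has leukocytes without a differential or lymphocyte count.

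The cost is a wording amendment, a line of CRF guidance and a little derivation from values already collected. The severity table may look less favourable.
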